[name]

Study protocol

19 Oct 2012

- The effect of per oral immunotherapy treatment in severe IgE mediated egg, milk and nut allergy in adults.

NCT01822353

[name]

Study protocol

19 Oct 2012

- The effect of per oral immunotherapy treatment in severe IgE mediated egg, milk and nut allergy in adults.

NCT01822353

Summary

Prospective study on per oral immunotherapy treatment in IgE mediated egg, milk and nut allergy in adults (18-50- year olds).

1. Aims

We aim to analyse the results of per oral immunotherapy treatment in severe egg, milk and nut allergy in adults.

Could severe egg, milk and nut allergy be treated with oral immunotherapy treatment in stead of total allergen avoidance and could desensitization thus be achieved?

2. Study plan

2.1. Subjects

We study up to 90 subjects. All subjects are adults having no other severe chronic diseases. The subjects belong to four different groups:

- (a) **30** 18-50 year olds who start per oral immunotherapy treatment in severe egg allergy.
- (b) **30** 18-50_year olds who start per oral immunotherapy treatment in severe milk allergy.

- (c) **30** 18-50 year olds who start per oral immunotherapy treatment in severe nut allergy.

The diagnosis of milk or egg allergy is verified with positive history, skin prick test, allergen specific IgE antibodies. In addition, food allergy is verified with an allergen specific challenge test.

Atopic subjects may have simultaneously other allergies. Intermittent mild asthma, and mild and moderate persistent asthma are tolerated and treatment with inhaled steroids and other asthma medication is allowed. Atopic subjects may have additional skin symptoms. Quality of life, anxiety and patient history data is collected by questionnaires. All patients undergo a spirometry with a bronchodilator test, exhaled nitric oxide and a methacholine challenge before and a year after oral immunotherapy. Those with test results diagnostic for asthma (FEV1 response in a bronchodilator test > 12%/200ml and/ or PD20 <600 µg/ml methacholine in methacholine provocation test) are treated with asthma medication before hyposensibilisation treatment is started.

Exclusion criteria: adults with instable cerebrovascular or heart disease, active autoimmune disease or cancer, or use of betablocking agents. In addition, poorly controlled asthma or FEV1 < 70% are not tolerated.

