2.3. Study protocol

Increasing doses are given daily. The first dose is given at the hospital and observed. Pre-specified other doses are also given observed at the hospital but otherwise oral food immunotherapy is continued at home.

All the patients undergoing oral immunotherapy are prescribed with emergency medication such as antihistamine tablets, prednisolon tablets (40mg for three days in adults), epinephrine autoinjector (300 µg per dose) and salbutamol or terbutaline inhalator.

After escalating doses of allergen during the first phase of oral immunotherapy, the treatment is continued with the highest tolerated maintenance dose until one year of therapy. Spirometry with a bronchodilator test, exhaled nitric oxide, a methacholine challenge and immunological parameters are studied a year after oral immunotherapy.

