- The effect of per oral immunotherapy treatment in severe IgE mediated egg, milk and nut allergy in adults.

NCT01822353

- The effect of per oral immunotherapy treatment in severe IgE mediated egg, milk and nut allergy in adults.

NCT01822353

3. Statistical methods

Frequencies, means, medians, proportions and standard deviations are calculated for all the data. Pairwise IgE results, methacholine challenge test results are analyzed using the nonparametric Wilcoxon signed rank test. Comparison of groups is done with chi square test and comparison of other continuous variables is done with t-test or with Mann-Whitney test. A p-value of less than 0.05 is considered statistically significant. The analyses will be performed using the SPSS 19.0 software package (SPSS Inc., Chicago, IL, USA).

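### Protocol section 2.1 states the methacholine cut-off for asthma medication as a PD20 in µg/ml, a concentration unit that does not fit a dose index

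*Protocol*

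**What the plan says.** Protocol section 2.1 schedules airway testing for everyone: "All patients undergo a spirometry with a bronchodilator test, exhaled nitric oxide and a methacholine challenge before and a year after oral immunotherapy". It then sets two criteria for results that count as diagnostic of asthma. One is a bronchodilator response in FEV1 above 12%/200 ml. The other is "PD20 <600 µg/ml methacholine in methacholine provocation test". The two are joined by and/or, and subjects who qualify "are treated with asthma medication before hyposensibilisation treatment is started".

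The methacholine test is named in two further places. Protocol section 2.3 repeats it at one year: "a methacholine challenge and immunological parameters are studied a year after oral immunotherapy". The SAP (section 3, Statistical methods) says that "methacholine challenge test results are analyzed using the nonparametric Wilcoxon signed rank test". Neither gives a unit or a cut-off.

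**The concern.** PD20 and µg/ml are different kinds of quantity. The documents do not define PD20. In its standard meaning it is the dose of the agent that provokes a 20% fall in FEV1, and a dose is a mass. A figure in µg/ml is a mass per volume, the form used for a provocative concentration (PC20). One of the two, label or unit, must be wrong.

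This matters more than a slip in background text would, because the line is a working rule. Through the and/or, the methacholine result can by itself put a subject on asthma medication before the food allergen is started. It is also the only numeric methacholine criterion in either document. A rule of this kind should be readable in only one way.

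**Working it through.** The plan has no figure here to reproduce. The check is one of dimensions, followed by a search for any text that settles the unit.

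**1. Dimensions.**
- Index as written: PD20, a dose (mass, e.g. µg).
- Unit as written: µg/ml, a concentration (mass per volume).
- These do not match.

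**2. The two possible readings.**
- Reading A: the label is right and the /ml is stray, giving PD20 < 600 µg.
- Reading B: the unit is right and the label is wrong, giving PC20 < 600 µg/ml. In the more usual unit, 600 µg/ml ÷ 1000 µg per mg = 0.6 mg/ml.

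**3. Are A and B the same threshold?** In the simplest case, dose = concentration × volume delivered. The two cut-offs then coincide only if the volume is 600 µg ÷ 600 µg/ml = 1 ml. The documents give no delivered volume, solution concentration or dose steps. A and B therefore cannot be treated as two spellings of one rule, and the gap between them cannot be calculated.

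**4. Does another place settle it?**

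| Place | What it says about methacholine | Unit or cut-off |
|---|---|---|
| Protocol 2.1, test schedule | Done at baseline and at one year | None |
| Protocol 2.1, asthma criteria | The disputed line | PD20, 600 µg/ml |
| Protocol 2.3 | Repeat at one year | None |
| SAP, Statistical methods | Paired Wilcoxon test | None |

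Nothing corrects or confirms the line. Section 2.3 does express the epinephrine autoinjector dose as a plain mass (300 µg). That is in keeping with reading A but says nothing about methacholine.

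**5. Where could the unit reach?**
- *Medication before immunotherapy.* The unit can alter this decision only for a subject who does not meet the bronchodilator criterion, is not already on the medication covered by "treatment with inhaled steroids and other asthma medication is allowed", and has a result on different sides of the cut-off under A and B. The last condition cannot be evaluated without the delivered volume.
- *Exclusion.* The asthma-related exclusion is that "poorly controlled asthma or FEV1 < 70% are not tolerated". It does not use the methacholine cut-off.
- *Paired analysis.* The signed rank test uses each subject's change and no cut-off. If one index is used at both visits, relabelling the unit multiplies every difference by the same positive constant, so signs and ranks stay as they are.

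**The case against.** The strongest reply is that this is a copy-edit. The text names its index, PD20, and gives a single number. Reading B needs the authors to have written the wrong index, and neither document mentions PC20 or a concentration endpoint. Staff who run the test would very probably take 600 as a dose in µg and never notice the /ml. Nothing is miscalculated, and no wrong decision is demonstrated.

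Most of that stands. Reading A is the likely one, and this is a unit inconsistency, not an arithmetic error. What does not follow is that the line can be left alone. The protocol is the controlling text for the decision, and a reader cannot confirm the intent from it.

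Three stronger readings are tempting, and the documents support none of them:
- *Some subjects were, or would be, wrongly treated or left untreated.* That requires staff to judge a result against an index other than the one named. Nothing suggests they would.
- *The error affects every enrolled subject, since all have a baseline test.* The number tested is not the number of decisions changed, and the latter cannot be derived.
- *The methacholine analysis is compromised.* The test uses no cut-off. The cut-off could reach the one-year comparison only through who receives medication, which again presupposes a changed decision.

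**Conclusion.** The point holds as a unit inconsistency in a decision threshold, of minor severity. The cut-off as printed pairs a dose index with a concentration unit, it can trigger treatment on its own, and no other text in the protocol or SAP resolves it. The probable intent is 600 µg.

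No size can be put on it: the documents show no altered treatment decision and do not allow a count of subjects at risk of one. Nor do they show any consequence for exclusion, the paired Wilcoxon test or the trial's conclusions.

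The verdict rests on two assumptions: that PD20 carries its standard meaning of provocative dose, and, for the analysis being untouched, that the same index is recorded at baseline and at one year.

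**What to change.** Check once against the laboratory's methacholine procedure, then correct the line in protocol section 2.1 to **PD20 < 600 µg**. If, and only if, the laboratory reports a concentration, change label and unit together to **PC20 < 0.6 mg/ml**. Do not describe the dose as cumulative unless the laboratory confirms that it is.

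The cost is one query and one line of text. No procedure, data item or SAP wording changes.

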2.2. Allergen specific challenge test

Increasing doses are given every 60 minutes during the food allergen challenge. After the last dose, patients are observed at least for 2 hours. The protocol is done in a double-blind manner (day A, day B) in peanut and egg allergy and in one-day open manner in milk allergy.

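### Does the undefined word 'nut' leave group (c) without a usable entry definition or challenge format?

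*Protocol*

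**What the plan says.** The study label is the same throughout the front matter. The protocol title reads "The effect of per oral immunotherapy treatment in severe IgE mediated egg, milk and nut allergy in adults", and the summary and section 1 (Aims) name the same three foods. In section 2.1, group (c) consists of 30 adults "who start per oral immunotherapy treatment in severe nut allergy". None of these places says whether the word covers peanut, tree nuts or both.

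Section 2.1 then gives two sentences on diagnosis. The first is limited to two foods: "The diagnosis of milk or egg allergy is verified with positive history, skin prick test, allergen specific IgE antibodies". The second is not limited: "In addition, food allergy is verified with an allergen specific challenge test".

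Section 2.2 sets the format of that challenge: "double-blind manner (day A, day B) in peanut and egg allergy and in one-day open manner in milk allergy". This is the only place in either document where peanut is named. Section 2.4 takes serum for allergen-specific and component IgE before treatment and at one year, with no restriction to particular foods.

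SAP section 3 analyses paired IgE and methacholine results with the Wilcoxon signed rank test and compares groups with standard tests. It neither defines the nut group nor divides it.

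Section 2.1 also announces the list of groups with "The subjects belong to four different groups" and then lists three.

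**The concern.** Three features together make group (c) look poorly defined. The label is broad, the first diagnostic sentence passes over it, and the challenge section uses a narrower word. A strict reader could ask which nuts qualify, whether history, skin prick test and IgE are entry requirements for this group, and what challenge format applies to a patient whose allergy is to a nut other than peanut. The mismatch in the number of groups adds to the doubt, since it leaves open whether a further group was once intended.

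If these doubts had force, two investigators could enrol different kinds of patient into a third of the study. The aim on desensitization in nut allergy would then be answered for an unclear mixture of foods. If several nuts were enrolled, the number per nut would fall below 30, and a paired test within one nut could have very little power.

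**Working it through.** The plan states no figure on this point to reproduce. The main check is a comparison of the texts, followed by three short calculations.

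**What covers each group**

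| Requirement | Egg (a) | Milk (b) | Nut (c) |
|---|---|---|---|
| IgE-mediated disease (title, summary) | yes | yes | yes |
| History, skin prick test, specific IgE (2.1, first diagnostic sentence) | named | named | not named |
| Challenge test (2.1, second diagnostic sentence) | yes | yes | yes |
| Challenge format (2.2) | named | named | named as peanut |
| IgE before treatment and at one year (2.4) | yes | yes | yes |

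Only one row is empty for group (c), and it is partly filled by others. IgE is measured at baseline anyway, and the disease must be IgE mediated. What is left unwritten is history and skin prick testing, and IgE as a formal entry condition, for patients whose allergy must still be verified by challenge.

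**Nut against peanut.** There are three groups and three foods with a format. Two match by name, which leaves nut and peanut to match each other. On that reading section 2.2 is complete. The documents do not prove it, but neither mentions tree nuts or a plan to enrol several kinds of nut. The two words do not contradict each other, since one may simply be narrower.

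**Group count.** 3 × 30 = 90, which equals the stated maximum, so a fourth group would have 90 − 90 = 0 places. The list and the total agree with each other, and only the word for the count is out of line. This is a clerical slip and says nothing about what nut means.

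**Reach.** Group (c) is 30/90 = 33% of the planned patients. That is the size of the group, not of an effect. The number with a nut other than peanut is not stated; the possible range is 0 to 30.

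**Small numbers within one nut.** Suppose a nut had n patients whose IgE all changed in the same direction, with no ties.

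- Exact signed rank test: the smallest two-sided p is 2/2ⁿ. For n = 5 this is 2/32 = 0.0625; for n = 6 it is 2/64 = 0.031.
- Normal approximation without continuity correction, n = 5: the rank sum is 15, its mean 5 × 6/4 = 7.5 and its variance 5 × 6 × 11/24 = 13.75. Then z = 7.5/√13.75 = 2.02 and p = 0.043.
- Normal approximation with continuity correction, n = 5: z = 7.0/√13.75 = 1.89 and p = 0.059.

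Whether five patients could reach 0.05 therefore depends on the version of the test, which the SAP does not name. The question does not arise in the planned analysis, because the SAP plans no test within a single nut.

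**The case for a change.** The strongest case for acting is that this wording is the case definition for a third of the patients, and that no other section settles it. Even if nut means peanut, the title, aims and group (c) use a wider word than the food tested, and the first diagnostic sentence still leaves group (c) out. The correction would cost a few words and no visits. The SAP also compares groups and tests paired IgE, so the make-up of group (c) and the IgE specificity measured in it bear on planned results.

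The textual part of this stands: the term is undefined, and the omission in section 2.1 is there to see. The consequences do not follow.

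- The published report can name the foods actually given, whatever the protocol called them, so readers need not be left guessing.
- The paired tests compare each patient with himself or herself. Provided the same allergen is measured at both times, which section 2.4 implies, a mixture of nuts does not bias the within-patient change.
- The heavier consequences require several nuts to be enrolled and reported separately. Neither document describes this.

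**Conclusion.** The observation is accurate, but it is an ambiguity and an omission, not a contradiction, and it calls for no change to the plan. If nut means peanut, all that remains is inconsistent terminology and one diagnostic sentence that leaves out a food. If it means more than peanut, group (c) patients must still have IgE-mediated allergy verified by challenge, with IgE measured before treatment and at one year. What is missing then is the challenge format for those patients, a detail that study staff would have to settle and record.

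The point touches at most 30 of 90 patients (33%), with 0 to 30 having a nut other than peanut. No bias in any planned analysis has been shown. The small-sample limit belongs to an analysis that the SAP does not contain, and at n = 5 it depends on an unstated choice of test version. The number of groups is a slip that the list and the total of 90 resolve.

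This rests on two assumptions: that the general challenge sentence in section 2.1 applies to group (c), as its wording indicates, and that the report will name the foods used. Clearer wording would help the reader but would alter neither who is analysed nor how.

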2.3. Study protocol

Increasing doses are given daily. The first dose is given at the hospital and observed. Pre-specified other doses are also given observed at the hospital but otherwise oral food immunotherapy is continued at home.

All the patients undergoing oral immunotherapy are prescribed with emergency medication such as antihistamine tablets, prednisolon tablets (40mg for three days in adults), epinephrine autoinjector (300 µg per dose) and salbutamol or terbutaline inhalator.

After escalating doses of allergen during the first phase of oral immunotherapy, the treatment is continued with the highest tolerated maintenance dose until one year of therapy. Spirometry with a bronchodilator test, exhaled nitric oxide, a methacholine challenge and immunological parameters are studied a year after oral immunotherapy.

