2.4. Immunological parameters

Serum samples are taken for allergen specific and allergen component evaluation (IgE) before oral immunotherapy and at one year after starting the therapy.

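### Does the differently worded one-year follow-up in Protocol 2.1, 2.3 and 2.4 leave the two paired tests without a defined time point?

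*Protocol*

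**What the plan says.** Three protocol sections time the follow-up measurements.

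- **Section 2.1** plans spirometry, exhaled nitric oxide and "a methacholine challenge before and a year after oral immunotherapy".
- **Section 2.3** first says how long treatment lasts: "the treatment is continued with the highest tolerated maintenance dose until one year of therapy". Its next sentence lists spirometry, exhaled nitric oxide, methacholine and immunology together and gives them one time: "immunological parameters are studied a year after oral immunotherapy".
- **Section 2.4** covers serum only. IgE samples are taken "before oral immunotherapy and at one year after starting the therapy".

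The SAP's section on statistical methods adds: "Pairwise IgE results, methacholine challenge test results are analyzed using the nonparametric Wilcoxon signed rank test". It does not name the visit that supplies the second value of each pair, and neither document gives a visit window. On size, section 2.1 says "We study up to 90 subjects", in three listed groups of 30.

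**The concern.** Section 2.4 counts its year from the start of therapy. The phrase in 2.1 and 2.3 does not say whether it counts from the start or the end, and in 2.3 it directly follows a sentence saying when the treatment year finishes. Taken literally, it puts follow-up a year after treatment stops.

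The date of the second measurement is part of what a before-and-after test estimates. A change measured at the end of a year on treatment answers a different question from a change measured a year later, and the documents do not say what happens to treatment after month 12. The IgE and methacholine comparisons are the only measures the SAP names for a paired test, so the ambiguity would touch both. If staff followed 2.4 for blood and the literal phrase for lung tests, the IgE change would span 12 months and the methacholine change 24.

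**Working it through.** The plan states no figure to reproduce. The check is calendar arithmetic, followed by a test of which reading the three sections can share.

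**Inputs**

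- Start of therapy: month 0.
- Planned end of therapy: month 12 (Protocol 2.3, counting escalation within the year).
- IgE follow-up: month 12 (Protocol 2.4).
- Lung tests and immunology share one time (Protocol 2.3).
- Subjects: 3 × 30 = 90 at most (Protocol 2.1).

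**Step 1. Date the loose phrase**

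- Counted from the start: 0 + 12 = month 12.
- Counted from the end of the planned year: 12 + 12 = month 24.

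**Step 2. Compare with section 2.4** (gap = date of the loose phrase − 12)

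- From the start: 12 − 12 = 0 months.
- From the end: 24 − 12 = 12 months.

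For a patient who completes the year, the gap is therefore 0 or 12, with nothing between. Intermediate values need early stopping combined with the end-of-therapy reading. As an illustration, stopping at month 3, 6 or 9 (assumed; not in the documents) gives follow-up at month 15, 18 or 21, and gaps of 3, 6 or 9 months.

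**Step 3. Which reading fits all the sections?**

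| Reading | Serum by 2.3 | Serum by 2.4 | Lung tests | Consistent? |
|---|---|---|---|---|
| Loose phrase counts from the start | 12 | 12 | 12 | Yes |
| Loose phrase counts from the end | 24 | 12 | 24 | No: 2.3 and 2.4 differ by 12 months on serum |
| Serum follows 2.4, lung tests count from the end | 12 | 12 | 24 | No: breaks the single common time in 2.3 |

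Only the first row holds together. The third row is the one behind the 12-against-24-month mismatch, and it splits a list that 2.3 dates as a unit.

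**Step 4. Is a later visit planned anywhere?** No. Neither document describes a phase after treatment, a month-24 visit or an off-treatment assessment.

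**Step 5. Are the pairs determined?** Sections 2.1 and 2.4 each give one occasion before therapy and one at a year. With two occasions per measure, a paired test has only one pair to use, so the SAP's silence on the visit leaves the analyst nothing to choose.

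**Step 6. Does anything depend on aligning the two measures?** The SAP tests IgE and methacholine separately and plans no correlation or comparison of the two changes. Even with different dates, each test would remain a valid before-and-after comparison of its own measure.

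**The case for a change.** The strongest reply is that plausible intent is not a specification. No passage equates the two phrases. Section 2.4 fixes the date of serum alone, so the date of the methacholine challenge, spirometry and exhaled nitric oxide is reached only by way of the shared sentence in 2.3. The literal phrase also sits right after a statement of when treatment ends, which invites the later reading. The remedy would cost very little: two phrases aligned, a window added, and one sentence in the SAP.

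The arithmetic stands, and so does the point that the methacholine date is inferred. The consequence does not. The inference is short and has no competitor that respects all three sections. The documents' silence on treatment after month 12 is better read as a sign that no assessment was planned there than as a further gap. A missing visit window is a separate and ordinary omission of detail; it does not show that the anchors conflict. A low cost is also no reason for a change when the edit would leave the data collected and the tests performed exactly as they are.

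One qualification concerns the length of the treatment year. If it counted maintenance only, the literal reading would fall later still: an assumed escalation of 1 to 8 months gives gaps of 13 to 20 months. That would enlarge the contradiction on the end-of-therapy reading. It would leave the start-anchored reading at month 12, still in agreement with 2.4.

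**Conclusion.** The concern does not call for a change. Sections 2.1 and 2.3 are loosely worded beside 2.4, but read together they settle on month 12 from the start of therapy. On that reading the gap is 0 months, both paired tests use the value before therapy and the one-year value, and no result changes for any of the up to 90 subjects. The 12-month gap arises only on readings that set 2.3 against 2.4 or break up the common time in 2.3.

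This rests on two assumptions: that the immunological parameters in 2.3 are the IgE measurements described under that heading in 2.4, and that no follow-up beyond the treatment year was intended, since none is described. This is a drafting slip that a competent analyst resolves from the protocol itself. Carrying the wording of 2.4 into the other two sections would be harmless tidying, with no effect on the analysis.
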